# 9.2 Visit 2 (Day $8 \pm 2$ ): Follow-Up

At this visit, the investigator or designee will:

Observe/query the subject about any changes in his/her health since the previous study visit. Initiate/update the appropriate AE form as required.

- Review the subject's compliance with the study requirements, including twice daily application of test article as directed at Visit 1.
- Query the subject about any changes in concomitant medications/therapies (including the bland emollient and the investigator-approved medicated shampoo as appropriate) since the previous study visit and document the findings.
- Record LSRs associated with topical application of the test article (see Section 10.5).
- Perform photography, at the discretion of the investigator (selected study sites only; see Section 11).
- Perform clinical evaluations (IGA and clinical signs of psoriasis; see Section 10).
- Document the percent BSA with active psoriasis in the Treatment Area. This will include any remaining lesions identified at the Baseline Visit AND any new psoriatic lesions that may be present at this visit.
- Review subject instructions on the proper application of the test article (Appendix 1) as well as review (and discuss any discrepancies or concerns with the subject regarding their use of the diary), collect, and dispense another (new) Subject Diary (Appendix 2) and review completion instructions.
  - o Instruct the subject to continue twice daily application of the test article as instructed to all psoriatic plaques in the Treatment Area.
- Collect and weigh used canisters of test article and weigh/dispense an additional canister of test article if necessary (see Appendix 4).
- Dispense bland emollient, as required.

<sup>13 Two applications of test article should be applied each day (approximately 8 hours or more separation between dose applications). If Visit 1 occurs in the late afternoon or evening, only one application will be possible on Day 1 and the time of this first application should be recorded on the Subject Diary (Appendix 2).

• Re-instruct the subject on the proper application of the test article and bland emollient. If necessary, to enhance compliance and proper application of the test article, the site may supervise test article application at this visit.

• Schedule Visit 3 (Day 15 + 3). Subjects should be instructed not to apply the test article within 4 hours prior to the scheduled final clinic visit.

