### 9.3 Visit 3 (Day 15 + 3): Final Visit

These activities may occur as scheduled at the end of the treatment period or earlier if the subject is to be dropped from the study.

At this visit, the investigator or designee will:

- Observe/query the subject about any changes in his/her health since the previous study visit. Initiate/update the appropriate AE form as required.
- Review the subject's compliance with the study requirements.
- Query the subject about any changes in concomitant medications/therapies (including the bland emollient and the investigator-approved medicated shampoo as appropriate) since the previous study visit and document the findings.
- Record LSRs associated with topical application of the test article (see Section 10.5).
- Perform photography (selected study sites only; see Section 11).
- Perform clinical evaluations (IGA, clinical signs of psoriasis, and pruritus; see Section 10).
- Record the location of remaining plaques in the Treatment Area in the CRFs.
- Document the percent BSA with active psoriasis in the Treatment Area. This will include any remaining lesions identified at the Baseline Visit AND any new psoriatic lesions that may be present at this visit.
- Perform a UPT for all WOCBP.
- Collect and weigh all canisters of used/unused test article (see Appendix 4).
- Review the subject's diary for completeness of doses applied and times of application. Ask the subject if they applied the test article prior to the clinic visit.
- Discharge subject from the study.

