### 10.1 Investigator's Global Assessment (IGA)

The IGA score is a static evaluation of the overall or "average" degree of severity of a subject's disease, taking into account all of the subject's psoriatic lesions (excluding those on the face, scalp, groin, axillae, and other intertriginous areas) by the investigator or designee as the subject appears on the day of the evaluation. This evaluation takes into consideration the three individual characteristics of psoriasis (scaling, erythema, and plaque elevation) with the IGA score at each visit representing the average degree of scaling, erythema, or plaque elevation that is present amongst all of the lesions eligible for treatment.

The investigator should NOT refer to any other assessments to assist with this evaluation. This evaluation is NOT a comparison with the IGA at any other visit or a mathematical calculation based on the clinical signs of psoriasis scores. The Visit 1 assessment must be made PRIOR to the first application of the test article and subsequent assessments should be made four hours or more after any application of the test article. At every study visit, evaluate all active psoriasis plaques (excluding those on the face, scalp, groin, axillae and other intertriginous areas) and report the one whole integer score that describes the average IGA using the following scale:

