## 13.2 Subject Discontinuation

A subject may be withdrawn from the study prior to completion for any of the following reasons:

- Whenever the subject decides it is in the subject's best interest to withdraw. NOTE: if the subject decides to withdraw from the study due to an AE then it should be classified as withdrawal due to an AE.
- Whenever the investigator decides it is in the subject's best interest to be withdrawn

- AEs
- Worsening of condition or treatment failure (in the opinion of the investigator)
- Intercurrent illness which may, in the investigator's opinion, significantly affect assessment of clinical status
- Noncompliance
- Pregnancy
- Lost to follow-up
- Sponsor administrative reasons

If a subject withdraws from the study prematurely for any reason, complete the final visit procedures. When a subject is withdrawn from the study for a treatment-related AE (i.e., possibly, probably or definitely related as defined in Section 14), when possible, the subject should be followed until resolution or stabilization of the AE.

Subjects who are prematurely withdrawn or discontinued from the study will not be replaced.

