#### 17.3 Statistical Methods

All statistical processing will be performed using SAS® unless otherwise stated. Statistical significance for the primary efficacy endpoint will be based on a two-tailed test of the null hypothesis at the alpha=0.05 level of significance.

Efficacy analyses will be performed primarily for the intent-to-treat (ITT) population. Efficacy analyses using the per-protocol (PP) population will be in support of the ITT analyses.

The Safety population will include all subjects enrolled in the study who were dispensed and applied test article at least once. Subjects will apply their first application of test article in the clinic during their Baseline Visit on Day 1. Subjects enrolled in the study who were

randomized and dispensed the test article will be considered the ITT population. Subjects will be included in the PP efficacy analyses if they have completed the study without significant protocol deviations. Subjects who discontinue from the study prematurely due to treatment failure, as determined by the investigator, will also be included in the PP population as treatment failures.

Demographic and baseline characteristics will be summarized by treatment group for the ITT, PP, and Safety populations. Frequency counts and percentages will be reported for categorical data and the number of subjects with non-missing data (n), mean, median, SD, minimum and maximum will be reported for the continuous variables.

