### 17.3.1 Efficacy Analyses

## 17.3.1.1 Primary Efficacy Analysis

Efficacy will be demonstrated if the proportion of HBP Foam treated-subjects with IGA "treatment success" at Day 15 is statistically significantly greater than the proportion of VEH Foam-treated subjects that are "treatment successes" at Day 15 based on a two-sided test at the alpha=0.05 level of significance. The treatment groups will be compared with respect to IGA treatment success rates at Day 15 using the CMH test stratified by center.

Subjects without data at Day 15 will be considered to be treatment failures (i.e., to not have achieved the primary endpoint). Note: this definition includes subjects who drop out of the study prior to Day 15 for any reason.

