#### 17.5 Sensitivity Analyses

Sensitivity analyses will be performed to investigate the impact of data imputation on the primary endpoint (IGA "treatment success" at Day 15). These sensitivity analyses will include repeating the primary analysis (IGA "treatment success" at Day 15):

- 1) in the population of subjects with observed data for the primary endpoint (i.e., the "complete cases" population);
- 2) in the per-protocol population;
- 3) assuming that subjects with missing data are responders ("treatment success");
- 4) assuming that subjects in the VEH Foam group with missing data are responders and that subjects in the HBP Foam group with missing data are treatment failures ("worst case"):
- 5) Using multiple imputation to impute missing values of the primary endpoint.

These analyses will be examined in conjunction with the reasons for dropout or the proportions of dropouts between treatment groups. Conclusions regarding the investigation of possible bias introduced by dropouts and/or the method of missing data imputation will be included in the final clinical study report.

For the sensitivity analysis based on multiple imputation, missing values of the primary endpoint will be imputed using the logistic regression methodology of SAS procedure MI. The logistic regression model will include the following independent variables: treatment and plaque elevation as the covariate. A minimum of 10 imputed data sets will be generated for this analysis. The MIANALYZE procedure of SAS will be used to combine the results.

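### The multiple-imputation sensitivity analysis omits the Day 8 IGA; if plaque elevation means the Baseline score, it nearly repeats the complete-case analysis

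*Combined protocol and SAP*

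**What the plan says.** Section 17.5 sets five sensitivity analyses for missing Day 15 IGA results: complete cases, per-protocol, all missing as responders, worst case, and multiple imputation. For the last, "missing values of the primary endpoint will be imputed using the logistic regression methodology of SAS procedure MI", and "The logistic regression model will include the following independent variables: treatment and plaque elevation as the covariate". The visit for plaque elevation is not stated. Day 8 IGA, Baseline IGA and center are not listed.

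The Day 8 IGA is available. The Visit 2 instruction in Section 9.2 reads "Perform clinical evaluations (IGA and clinical signs of psoriasis; see Section 10", and Section 10.1 says "At every study visit, evaluate all active psoriasis plaques".

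On early leavers, Section 9.3 lets the final-visit activities take place "earlier if the subject is to be dropped from the study", and Section 13.2 says "If a subject withdraws from the study prematurely for any reason, complete the final visit procedures". For the primary analysis, Section 17.3.1.1 treats subjects without Day 15 data as failures and notes that "this definition includes subjects who drop out of the study prior to Day 15 for any reason". Section 17.5 does not say whether an IGA from an early final visit is observed Day 15 data in analyses 1 and 5. Under Section 17.3, early leavers whom the investigator judges to be treatment failures "will also be included in the PP population as treatment failures".

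**The concern.** Multiple imputation adds to a complete-case analysis only if the model contains something that predicts both the missing result and the loss. Treatment and a Baseline sign score offer little of either. The Day 8 IGA is the obvious candidate, since it is the same scale one week earlier.

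Baseline is the natural reading of plaque elevation because only that score is normally complete and no step is given for imputing a covariate. On that reading, agreement between analyses 5 and 1 is close to automatic. Section 17.5 says these analyses will support the report's conclusions on dropout bias, so that agreement could be taken for corroboration. The status of an early final-visit IGA also matters, because it decides how many values are imputed.

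**Working it through.** **Plan's own figure.** The synopsis gives 200 per arm, 20% vs 9%, Fisher's exact test, two-sided 0.05, power 0.85. Exact enumeration gives 0.858, so it reproduces.

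**Inputs.** From the plan: 20%, 9% and 200 per arm. Assumed: Day 8 IGA improvers are 40% of HBP and 15% of VEH; Day 15 success is 40% (HBP) and 30% (VEH) in improvers, 6.67% and 5.29% in non-improvers.

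- HBP: 0.40×0.40 + 0.60×0.0667 = 0.20
- VEH: 0.15×0.30 + 0.85×0.0529 = 0.09
- SE = sqrt(0.20×0.80/200 + 0.09×0.91/200) = 3.48 points

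**One case in full.** Loss of 12% in non-improvers and 3% in improvers, both arms. The observed success rate in an arm is (retained successes)/(retained subjects).

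- HBP: (0.40×0.97×0.40 + 0.60×0.88×0.0667)/(0.40×0.97 + 0.60×0.88) = 0.1904/0.916 = 20.79%
- VEH: (0.15×0.97×0.30 + 0.85×0.88×0.0529)/(0.15×0.97 + 0.85×0.88) = 0.0833/0.8935 = 9.32%
- Complete-case difference: 11.47, an error of +0.47

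With an uninformative Baseline score, the imputation model returns the same 11.47. With Day 8 IGA added (main-effects logistic model fitted to observed subjects, then used for leavers) the result is 11.04. The numerators alone give the missing=failure difference, 10.7.

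**All cases** (difference in points; truth 11.00):

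| Loss, non-improver/improver | Missing HBP, VEH | Complete case | MI, Baseline reading | MI with Day 8 IGA | Missing=failure |
|---|---|---|---|---|---|
| 6%/1.5%, both arms | 4%, 5% | 11.23 | 11.23 | 11.02 | 10.86 |
| 12%/3%, both arms | 8%, 11% | 11.47 | 11.47 | 11.04 | 10.72 |
| 24%/6%, both arms | 17%, 21% | 12.01 | 12.01 | 11.09 | 10.43 |
| VEH 24%/6%, HBP 5% random | 5%, 21% | 10.28 | 10.28 | 11.05 | 11.35 |
| HBP 24%/6%, VEH 5% random | 17%, 5% | 12.73 | 12.73 | 11.05 | 9.53 |
| Random | 8%, 11% | 11.00 | 11.00 | 11.00 | 10.39 |

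The largest error, 1.73/3.48, is 0.50 SE.

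**If the Baseline score is prognostic** (odds ratio 0.67 to 0.33 on both Day 8 improvement and Day 15 success), the Baseline reading gives 11.37–11.46 (12%/3%), 11.78–11.98 (24%/6%), 12.42–12.70 (HBP only) and 10.29–10.36 (VEH only). It stays within about 0.3 points of complete case.

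**If loss does not follow Day 8 IGA itself.**
- Following Day 8 plaque elevation (12%/3%): 11.28 on the Baseline reading, 11.03 with Day 8 IGA.
- Following the unseen Day 15 result: 11.77 vs 11.59 (12%/3%, both arms), 12.72 vs 12.29 (24%/6%, both arms), 14.62 vs 13.97 (HBP only), 9.10 vs 9.32 (VEH only). Only about 12% to 25% of the error goes.

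**If half of leavers have an early final-visit IGA counted as Day 15** (and equal to it), the Baseline-reading error falls from +0.47 to +0.23 (12%/3%) and from +1.73 to +0.79 (HBP only).

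**Finite samples.** 3,000 simulated trials, 200 per arm, 10 imputations. At 12%/3% the correlation of Baseline-reading MI with complete case is 0.995; RMSE from the full-data result is 1.11, or 0.90 with Day 8 IGA. In the HBP-only case the figures are 0.993, and 2.14 vs 1.10.

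**Second simulation, different assumptions.** 1,500 trials, 20 imputations; Day 8 IGA of 0–1/2/3–4 in 40/45/15% of eventual successes and 3/25/72% of failures; Baseline plaque elevation odds ratio 0.7 per grade. Bias against full data, in points:

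| Loss by Day 8 IGA (0–1/2/3–4) | Complete case | Baseline plaque elevation | Day 8 plaque elevation | Day 8 IGA added |
|---|---|---|---|---|
| 2/5/15%, both arms | +0.56 | +0.56 | +0.16 | 0.00 |
| HBP 3/3/5%, VEH 2/5/25% | -1.06 | -1.10 | -0.37 | -0.05 |
| HBP 2/5/25%, VEH 10% random | +2.42 | +2.41 | +0.79 | +0.06 |
| HBP 25/10/3%, VEH 5% random | -1.60 | -1.58 | -0.58 | +0.01 |

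**The proposed model.** In a further simulation with five IGA levels (inputs again assumed), the Baseline reading matched complete case within 0.01 point, with errors of -1.45 to +1.69. The model proposed below, with linear scores, left at most 0.04 when loss followed Day 8 response.

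**The case against.** The case for leaving the text alone has real points.

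- *The reading is not certain.* If Day 8 plaque elevation was meant, about two thirds of the bias goes (+2.42 to +0.79 in the second table). This stands, and is itself a reason to name the visit. A Day 8 score would also need an imputation step that the plan lacks.
- *No decision is shown to change.* With loss depending on response in both arms, the error is 0.07 to 0.29 SE. The 0.50 SE case needs strong response-driven loss in HBP only. This stands.
- *The confirmatory test does not share the upward error.* In the four cases where analysis 5 is too high, missing=failure gives 9.53 to 10.86, below the true 11.0. This stands and limits the harm.
- *Other analyses address response-driven loss.* Analyses 3 and 4 do not use the model, per-protocol keeps investigator-judged treatment failures, and Section 17.5 has the results read alongside dropout reasons and rates. This is true, but subjects leaving after Visit 2 for other reasons still have a Day 8 IGA that analysis 5 ignores.
- *The Notes in Sections 17.3.1.1 and 17.4 largely settle the early final visit.* Mostly so, but they define failure for the primary and key secondary endpoints. Whether the value is observed in analyses 1 and 5 is left to inference.
- *The near-zero error after the change is partly built in*, because loss was generated from Day 8 IGA. This stands; the gain is small if loss follows the unseen Day 15 result.

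**Conclusion.** The concern holds, as a change that should be made to one supportive analysis. On the Baseline reading, analysis 5 tracks complete case almost exactly and carries the same error when loss depends on Day 8 response. In the first set of cases that error runs from -0.7 to +1.7 points on a difference of 11.0; under the second set of assumptions it runs from -1.6 to +2.4. It is zero if loss is random and small if loss is low. Apart from the 20% and 9% success rates and the 200 per arm, the inputs are assumed: the plan states neither a dropout rate nor a Day 8 to Day 15 relationship. The primary test and the worst-case analysis are unaffected. Confidence is medium because the visit is unstated and the loss mechanism unknown.

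**What to change.** In Section 17.5:

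1. Specify the endpoint model as treatment, Baseline IGA, Baseline plaque elevation and Day 8 IGA, each score as one linear term.
2. Impute a missing Day 8 IGA first, in monotone order, by predictive mean matching on treatment, Baseline IGA and Baseline plaque elevation, which keeps it on observed integer scores. If any subject has Day 15 but no Day 8 data, the pattern is not monotone; use fully conditional specification with the same two models.
3. Say explicitly that the center-stratified primary analysis is repeated on each completed data set, and name the quantity pooled. The repetition is already implied; the pooled quantity is not stated.
4. State whether an IGA from an early final visit counts as observed Day 15 data in analyses 1 and 5. Treating it as missing would match the Note in Section 17.3.1.1.

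The cost is revised wording, a few lines of code and one extra imputation step, on data already collected. The sentence sits in the protocol text, so if it is changed by protocol amendment, Section 18.4 requires IRB approval. Nothing is gained for subjects lost before Visit 2.

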#### 17.6 Multicenter Studies

Each center will conduct the clinical study under a common protocol. Consistency in study execution at each center will be emphasized. The study is to be conducted in such a manner as to have a minimum of eight ITT subjects enrolled in each of the HBP Foam and VEH Foam treatment groups at each center.

The exploratory analyses discussed in the remainder of this section will be conducted using only those centers with at least eight ITT subjects in each of the two treatment groups.

The consistency of treatment response across the centers will be analyzed using a Breslow-Day test to evaluate a treatment by center interaction in the analysis of the primary efficacy variable (IGA "treatment success"). If the Breslow-Day test is significant ( $p \le 0.10$ ), a sensitivity analysis that excludes centers with the extreme efficacy results will be performed to determine the robustness of the treatment effect. Otherwise, the data will be considered to be free of the impact of extreme centers.

Identification of an extreme center begins by analyzing all subsets that can be created by excluding one center. If one or more of the subsets result in a Breslow-Day test for interaction p-value > 0.10, then the center excluded from the subset with the largest p-value will be considered to be the extreme center.

If all of the subset p-values are  $\leq 0.10$ , the process will be repeated by excluding two centers. If one or more of these subsets result in an interaction p-value > 0.10, then the centers excluded from the subset with the largest p-value will be considered to be the extreme center. This process is repeated until the p-value exceeds 0.10.

Upon identification of the extreme center(s), the analysis of IGA "treatment success" continues with the remaining centers. Inferences will be based on this analysis in addition to observations regarding the extreme center(s). Conclusions will be presented as appropriate to the findings of the sensitivity analysis.

# 17.7 Multiple Comparisons/Multiplicity

Statistical significance for the primary efficacy endpoint (IGA treatment success at Day 15) will be based on a two-tailed test of the null hypothesis of no difference at the alpha=0.05 level of significance.

If the primary endpoint is statistically significant then the statistical significance testing for the three key secondary endpoints will use the "gatekeeping" approach (8) to control the overall level of significance.

Statistical significance testing for the other efficacy endpoints will be performed as supportive analyses for the primary and secondary endpoints and will not be adjusted for multiplicity concerns.

# 17.8 Subgroup Analyses

Treatment success rates (IGA) will be evaluated for subgroups based on gender (male/female), race (Caucasian/non-Caucasian) and age ( $<65 / \ge 65$ ). Treatment success rates (IGA) will be evaluated for subgroups based on gender (male/female), race (Caucasian/non-Caucasian) and age ( $<65 / \ge 65$ ).

#### 17.9 Interim Analyses

No interim analyses will be performed.

## 18. ETHICAL AND REGULATORY CONSIDERATIONS

### 18.1 Compliance with Good Clinical Research Practice

This study will be conducted in compliance with the principles of the Declaration of Helsinki, with the current Good Clinical Practice guidelines and with other applicable regulations. The investigator and all study staff will conduct the study in compliance with this protocol. The protocol, informed consent documents, recruitment advertisements and any amendments to these items will have IRB approval prior to study initiation. Voluntary informed consent will be given by every subject prior to the initiation of any study-related procedures. The rights, safety and well-being of the study subjects are the most important considerations and prevail over the interests of science and society. All personnel involved in the conduct of this study must be qualified by education, training and experience to perform their assigned responsibilities.

